GALDERMA	<small>Title</small> 43USSA1705 Sculptra Clinical Study Protocol	<small>Doc id</small> MA-37876
---	--	--

2019-02-21 18:33

Effective date:

A randomized, evaluator-blinded, multi-center study to evaluate the safety and effectiveness of Sculptra Aesthetic for correction of nasolabial folds

Study product: Sculptra® Aesthetic

Clinical trial number (CTN): 43USSA1705

Sponsor: Q-Med AB, a Nestle Skin Health Affiliate

Effective

Version: 5.0

 GALDERMA	Title 43USSA1705 Sculptra Clinical Study Protocol	Doc id MA-37876
---	---	---------------------------

2019-02-21 18:33

Effective date:

Study Administrative Structure

Sponsor: Q-Med AB, a Nestle Skin Health Affiliate
[REDACTED]
[REDACTED]
[REDACTED]

Global Head of Clinical
Development: [REDACTED]

Sponsor's Medical Expert: [REDACTED]

Sponsor's Scientific Writer: [REDACTED]

Sponsor's Clinical Project
Manager: [REDACTED]

Sponsor's Statistician: [REDACTED]

Effective

Version: 5.0

Further details on all participating Investigators and the complete administrative structure of the study are found in the study files. Note that administrative changes are to be documented in the study files without requiring a Clinical Investigational Plan (CIP) amendment.

Effective date: 2019-02-21 18:33

Effective

Version: 5.0

 GALDERMA	<small>Title</small> 43USSA1705 Sculptra Clinical Study Protocol	<small>Doc id</small> MA-37876
---	--	--

Sponsor Signatures

The CIP is electronically signed in the document management system within the Q-Med AB quality management system by the representatives listed below.

2019-02-21 18:33

Effective date:

Effective

Version: 5.0

Synopsis

Title of study	A randomized, evaluator-blinded, multi-center study to evaluate the safety and effectiveness of Sculptra Aesthetic for correction of nasolabial folds
Clinical Trial Number	43USSA1705
Countries involved	United States
Number of sites	Approximately 5 sites
Number of subjects	Approximately 80 total subjects will be enrolled in the study [REDACTED] [REDACTED] [REDACTED] [REDACTED]
Target Indication	Sculptra Aesthetic is indicated for use in immune competent people as single regimen for correction of shallow to deep nasolabial fold contour deficiencies and other facial wrinkles. The development proposed is within the approved indication to assess the safety and effectiveness after changes in reconstitution and injection procedures.
Safety Objective and Endpoints	The objective is to evaluate the safety of Sculptra Aesthetic as a single regimen for correction of Nasolabial Fold (NLF) contour deficiencies after changes in reconstitution and injection procedures compared to the approved label. Safety endpoints 
 • Incidence, intensity, time to onset and duration of adverse events collected throughout the study period. • Incidence, intensity, time to onset and number of days of pre-defined expected post-treatment events collected using subject

Effective date: 2019-02-21 18:33

Effective

Version: 5.0

	
diaries for 28 days from each treatment.
 
 • [REDACTED]
Effectiveness Objectives and Endpoints	
The objective is to evaluate the effectiveness of Sculptra Aesthetic as a single regimen for correction of NLF contour deficiencies after changes in reconstitution and injection procedures compared to the approved label.
 
Primary effectiveness endpoint
 
Change from baseline on both sides of the face as assessed by the Blinded Evaluator using [REDACTED] at 48 Weeks after the first treatment session.
 
[REDACTED] [REDACTED] [REDACTED] [REDACTED] [REDACTED] [REDACTED] [REDACTED]

Study Design	
This is a prospective, randomized, evaluator-blinded, multicenter US study.

Subject Participation	
A subject may be involved in the study for approximately 52 weeks from screening to the final follow-up visit.

Enrollment	
Written informed consent will be obtained before any study related procedures is performed. Subjects will be screened for eligibility within 30 days prior to injection. The screening visit and baseline visit may be performed on the same day. Subsequent to screening, eligible subjects will be randomized in the study.
 
[REDACTED]
 
This study will include at least eight (8) subjects with Fitzpatrick Skin Type (FST) IV and at least eight (8) subjects with FST V-VI.

Effective date: 2019-02-21 18:33

Effective

Version: 5.0

Inclusion criteria	
The subjects must meet the following criteria to be eligible for the study:
 
 1. Subjects willing to comply with the requirements of the study and providing a signed written informed consent. 2. Immune-competent men or women over 21 years of age 3. Intent to undergo correction of BOTH left and right NLFs 4. [REDACTED] 5. [REDACTED] 6. [REDACTED] 7. [REDACTED] 8. [REDACTED] 9. [REDACTED] 10. [REDACTED]
Exclusion criteria	
The presence of any of the following exclusion criteria will exclude a subject from enrollment in the study:
 
 1. Known/previous allergy or hypersensitivity to any of the Sculptra Aesthetic constituents. 2. Known/previous allergy or hypersensitivity to lidocaine and other local anesthetics, e.g. amide-type anesthetics, or topical anesthetics or nerve blocking agents. 3. Previous or present multiple allergies or severe allergies, such as manifested by anaphylaxis or angioedema, or family history of these conditions. 4. [REDACTED]

Effective date: 2019-02-21 18:33

Effective

Version: 5.0

5.

2019-02-21 18:33

Effective date:

Effective

Version: 5.0

GALDERMA	Title 43USSA1705 Sculptra Clinical Study Protocol	Doc id
		MA-37876

Investigational product, reference product, dose, mode of administration and location of treated area
 
Reconstitution with 8 mL of SWFI (Treatment group):
 
Sculptra Aesthetic (sterile, freeze-dried, injectable poly-L-lactic acid) is available in 367.5 mg dose vials and will be reconstituted prior to use by the addition of 8 ml of Sterile Water for Injection (SWFI) at the investigational site following the reconstitution instructions.
 
[REDACTED]
		

2019-02-21 18:33

Effective date:

Effective

Version: 5.0

Effective date: 2019-02-21 18:33

Effective

Version: 5.0

	
Evaluation of Safety:
 
Adverse Events (AEs) will be obtained from signs and symptoms reported by the subject or detected during each examination visit to obtain information about any medical occurrence that meets the definition of an AE.
 
[REDACTED]
 
[REDACTED]
 
[REDACTED]
 
Any subject with a treatment related AE that is ongoing at the time of study completion will be followed until that AE is resolved or stabilized. Any AE assessed as related to the study product or injection procedure with onset after subject participation in the study is over, and that the Investigator becomes aware of should be reported to the Sponsor.
 
All subjects will complete a Diary for 28 days after each treatment, to collect information about pre-defined, expected, post-treatment events at the treated area..
 
[REDACTED]
 
[REDACTED]
 
[REDACTED]

Study Procedures	
Study Report
 
A study report will be compiled at the conclusion of the study. This report will be included in the regulatory submission for marketing application.

Schedule of Events	
 • [REDACTED] – [REDACTED] – [REDACTED] – [REDACTED]

Effective date: 2019-02-21 18:33

Effective

Version: 5.0

	• [REDACTED]	[REDACTED]
	• [REDACTED]	[REDACTED]
	• [REDACTED]	[REDACTED]
Effectiveness assessments	• [REDACTED]	[REDACTED]
	• [REDACTED]	[REDACTED]
Safety Assessments	• [REDACTED]	[REDACTED]
	• [REDACTED]	[REDACTED]
Statistical Methods	[REDACTED]	[REDACTED]
	[REDACTED]	[REDACTED]

Effective

Effective date: 2019-02-21 18:33

Version: 5.0

Principles for the analysis

All results will be evaluated for the treatment group and reference group separately.

Effective date: 2019-02-21 18:33

Effective

Version: 5.0

 GALDERMA	Title 43USSA1705 Sculptra Clinical Study Protocol	Doc id MA-37876
--	---	---------------------------

Abbreviations and Definitions of Terms

AE	Adverse event
AESI	Adverse event of special interest
Blinded Evaluator	An evaluator responsible for independent evaluation of treatment result(s). The evaluator must not be involved in the treatment of the subject.
CE	French: Conformité Européenne
CFR	Code of Federal Regulations
Childbearing potential	A female (including pre-menopausal subjects) capable of becoming pregnant. This includes women on oral, injectable or mechanical contraception; women who are single, women whose husbands have been vasectomized or whose husbands have received or utilizing mechanical contraceptive devices.
CIP	Clinical Investigational Plan
CRF	Case report form
CRO	Contract research organization
CTA	Clinical trial agreement
CTN	Clinical trial number
CV	Curriculum vitae
Device deficiency	Inadequacy of a medical device with respect to its identity, quality, durability, reliability, safety or performance (includes malfunctions, use errors, and inadequate labelling)
DMP	Data management plan
eCRF	Electronic case report form
ET	Early Termination
FDA	United States Food and Drug Administration
First treatment	Initial injection of study product
FST	Fitzpatrick Skin Type
G	Gauge
GCP	Good Clinical Practice
HA	Hyaluronic acid
HIPAA	Health Insurance Portability and Accountability Act
HIV	Human Immunodeficiency Virus
ICF	Informed Consent Form
ICH	International Conference on Harmonisation
IFU	Instructions for use

 GALDERMA	Title 43USSA1705 Sculptra Clinical Study Protocol	Doc id MA-37876
--	---	---------------------------

Effective date: 2019-02-21 18:33

Effective

Version: 5.0

Investigational product	Medical device being assessed for safety or performance in a study. “Investigational product” is the same as “study device”, “investigational device”, or “investigational medical device”
Institution	Any public or private entity or agency or medical or dental facility where a clinical study is conducted.
Investigator	The Principal Investigator (PI) or other qualified person, i.e. sub-investigator, designated and supervised by the PI at a study site to perform critical study-related procedures or to make important study-related decisions as specified on the signature and delegation log
Investigator file	Essential documents relating to a clinical study as defined in applicable GCP guidance document and maintained by the Investigator.
IP	Investigational Product
IPL	Intense Pulsed Light
IRB	Institutional Review Board
ISO	International Organization for Standardization
IUD	Intrauterine Device
MedDRA	Medical dictionary for regulatory activities
Nasolabial Fold (NLF)	Lines between the nose and the corner of the mouth
NSAID	Non-Steroidal Anti-Inflammatory Drugs
PLLA	Poly-L-lactic acid

1.1 Statement of ethical compliance

The study shall be conducted in compliance with the Clinical Trial Agreement (CTA), the Clinical Investigational Plan (CIP), Good Clinical Practice (GCP), and applicable regional or national regulations. The study shall be conducted in accordance with the ethical principles that have their origin in the Declaration of Helsinki¹.

The study shall follow the international standard for clinical study of medical devices for human subjects, ISO14155 as applicable for US regulations and the International Conference on Harmonization (ICH) guideline for GCP (E6) as applicable for medical device.

1.2 Application to Institutional Review Board and/or Regulatory Authorities

It is the responsibility of the Principal Investigator (PI) to obtain approval of the CIP/CIP amendment from the Institutional Review Board (IRB). The study shall not begin until the required favorable opinion from the IRB has been obtained. The PI shall file all correspondence with the IRB in the Investigator file and copies of IRB approvals shall be forwarded to the Sponsor. Any additional requirements imposed by the IRB or regulatory authorities (RA), shall be followed.

The study requires application for approval from the US Food and Drug Administration (FDA). The study will not be started until the Sponsor has received written approval or until the statutory waiting period from the appropriate authority has elapsed.

The collection, access to, processing, and transfer of protected health information or sensitive personal data shall be carried out in accordance with applicable regional or national regulations.

2. Background Information

2.1 Indication and population description

[figure not shown]
 GALDERMA	<small>Title</small> 43USSA1705 Sculptra Clinical Study Protocol	<small>Doc id</small> MA-37876
---	--	--

Effective date: 2019-02-21 18:33

Effective

Version: 5.0

2.2 Investigational and Reference product description

2019-02-21 18:33

Effective date:

Effective

Version: 5.0

2.3 Clinical documentation

2.4 Study rationale and justification for design

the *labeled* and *unlabeled* data. The *labeled* data is used to train a model, while the *unlabeled* data is used to refine the model's predictions. This process is iterative, with the model's predictions being used to label the *unlabeled* data, which is then used to train the model further. This approach can be used to handle large amounts of data that are difficult to label manually, as it allows for the use of a small amount of labeled data to train a model that can then be used to label the rest of the data.

2019-02-21 18:33

Effective date:

Effective

Version: 5.0

2.5 Risks and benefits

A high-contrast, black and white image showing a series of horizontal bars. The bars are mostly black, with white gaps between them. The bars are of varying lengths and are positioned in a staggered, non-overlapping manner. The image is set against a white background.

 GALDERMA	<small>Title</small> 43USSA1705 Sculptra Clinical Study Protocol	<small>Doc id</small> MA-37876
---	--	--

2019-02-21 18:33

Effective date:

Effective

Version: 5.0

3. Objectives and Endpoints

3.1 Safety objective and endpoints

Safety objective

The objective is to evaluate the safety of Sculptra Aesthetic as a single regimen for correction of NLF contour deficiencies after changes in reconstitution and injection procedures compared to the approved label.

Safety endpoints

- Incidence, intensity, time to onset and duration of adverse events collected throughout the study period.
- Incidence, intensity, time to onset and number of days of pre-defined expected post-treatment events collected using subject diaries for 28 days from each treatment.
- [REDACTED]

	Title 43USSA1705 Sculptra Clinical Study Protocol	Doc id MA-37876
--	---	---------------------------

2019-02-21 18:33

Effective date:

Effective

Version: 5.0

3.2 Effectiveness objective and endpoints

Effectiveness objective

The objective is to evaluate the effectiveness of Sculptra Aesthetic as a single regimen for correction of NLF contour deficiencies

[REDACTED]

Primary effectiveness endpoint

- Change from baseline on both sides of the face as assessed by the Blinded Evaluator using [REDACTED] at 48 Weeks after the first treatment session.

[REDACTED]

[REDACTED]

[REDACTED]

[REDACTED]

[REDACTED]

[REDACTED]

[REDACTED]

4. Design of the Study

4.1 General outline

This is a 48-week, randomized, evaluator-blinded, parallel-group, multi-center, study to evaluate the safety and effectiveness of treatment with Sculptra Aesthetic for correction of NLF contour deficiencies after changes in reconstitution and injection procedures compared to the approved label.

Approximately 64 subjects requiring correction of NLFs will be enrolled and randomized in a 2:1 ratio to treatment with Sculptra Aesthetic reconstituted with 8 mL of SWFI (treatment group) or to Sculptra Aesthetic reconstituted with 5 mL of SWFI (reference group). In addition, eight (8) subjects with FST IV and eight (8) subjects with FST V-VI will be included but not randomized. These subjects will be treated with Sculptra Aesthetic reconstituted with 8 mL of SWFI. When these numbers of FST IV-VI have been treated, any additional FST IV-VI will be randomized in a 2:1 ratio (8 mL:5 mL).

Approximately 60 subjects will be treated with Sculptra Aesthetic reconstituted with 8 mL of SWFI and a reference group of approximately 20 subjects will be treated with Sculptra Aesthetic reconstituted with 5 mL of SWFI as according to the current label.

[REDACTED]

Investigator blinding will be accomplished by using a Treating Investigator to administer the

 GALDERMA	<small>Title</small> 43USSA1705 Sculptra Clinical Study Protocol	<small>Doc id</small> MA-37876
---	--	--

Effective date: 2019-02-21 18:33

treatments and a Blinded Evaluator, to whom randomization and treatment are concealed, to conduct the blinded assessments. In addition, the Blinded Evaluator should not be allowed to retrieve study supplies or be present during the opening of the study supplies or injection procedure. All documents with information regarding study products and randomization assignment should be kept in a separate binder not available to the blinded evaluator. Safety assessments will be performed by non-blinded personnel.

Eligible subjects randomized to receive treatment will be injected by the Treating Investigator at Day 1. The method of injection is at the discretion of the treating Investigator according to Sections 2.2 and 6.6.

Sufficient amount of product should be injected to achieve optimal correction of the NLFs, in the opinion of the Treating Investigator and subject.

Information will be collected about treatment procedure (e.g. injection technique, depth, injection volume, needle sizes, and anesthesia used).

*Effective*

Version: 5.0

Effective date: 2019-02-21 18:33

Effective

Version: 5.0

 GALDERMA	<small>Title</small> 43USSA1705 Sculptra Clinical Study Protocol	<small>Doc id</small> MA-37876
--	--	--

2019-02-21 18:33

Effective date:

Effective

Version: 5.0

4.2 Number of subjects

Approximately 80 subjects will be recruited at approximately 5 sites in the USA.

The duration of enrollment is expected to be approximately 3 months.

4.3 Duration of subject participation

A subject may be involved in the study for approximately 52 weeks from screening to the final follow-up visit.

End of study is when enrollment has reached the target number of subjects and all subjects have completed the last study visit.

4.4 Randomization and blinding

[REDACTED]

4.4.2 Blinding

Blinding will be accomplished by using a Treating Investigator to administer the treatments and a Blinded Evaluator, to whom randomization and treatment are concealed, to conduct the blinded assessments. The Treating Investigator will not be blinded. The Blinded Evaluator is not allowed to discuss treatments with the Treating Investigator or subjects. No study related documents that contain information regarding the treatment of subjects should be available to the Blinded Evaluator. Safety assessments will be performed by non-blinded personnel who are qualified by training and experience.

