### 1.3.5 Subject Diary

A subject diary will be dispensed to all subjects for daily completion for 28 days beginning on the injection day for each treatment with direct questioning for [REDACTED]

[REDACTED]	[REDACTED]

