### Subject Satisfaction

Answers on the subject satisfaction questionnaire will be summarized.

[REDACTED]

[REDACTED]

[REDACTED]

[REDACTED]

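### The legible blinding section masks only the Blinded Evaluator, so subjects may know their dilution and the subject-reported 8 mL and 5 mL results are open to reporting bias

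*Protocol*

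**What the plan says.** Protocol 4.1 describes the trial as follows: "This is a 48-week, randomized, evaluator-blinded, parallel-group, multi-center, study". The blinding section, 4.4.2, is legible and gives the mechanism: "Blinding will be accomplished by using a Treating Investigator to administer the treatments and a Blinded Evaluator, to whom randomization and treatment are concealed". It then says who is not masked. On the injector: "The Treating Investigator will not be blinded". On safety: "Safety assessments will be performed by non-blinded personnel who are qualified by training and experience". It adds one rule on communication: "The Blinded Evaluator is not allowed to discuss treatments with the Treating Investigator or subjects". Protocol 4.1 lists practical steps that keep supplies, the injection procedure and assignment papers away from the evaluator. No legible text gives a matching step for subjects.

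Subjects supply several outcomes. SAP 1.3.5 says: "A subject diary will be dispensed to all subjects for daily completion for 28 days beginning on the injection day for each treatment". Diary events are a named safety endpoint (Protocol 3.1, SAP 1.6), and SAP 2.5.4 presents days with each event by treatment group. SAP 2.4.4 calculates the proportion improved from the subject's own rating, by group with 95% confidence intervals, and separately from the Treating Investigator's rating. It also summarises the folds questionnaire by group. On satisfaction it says only: "Answers on the subject satisfaction questionnaire will be summarized".

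Not every 8 mL subject is randomised. Protocol 4.1 states: "In addition, eight (8) subjects with FST IV and eight (8) subjects with FST V-VI will be included but not randomized". All 16 receive the 8 mL preparation.

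**The concern.** The stated objective is to judge safety and effectiveness after a change in reconstitution, relative to the approved label. A subject who knows that he or she has the new or the labelled preparation may record symptoms, improvement and satisfaction differently for that reason alone. Analysis cannot remove that kind of bias. The observed-case and randomised-only sensitivity analyses in the SAP address missing data and the non-randomised subjects, not awareness of treatment.

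A subject who knows the dilution is also one possible route by which it could reach the evaluator, whose rating is the primary endpoint. The rule against discussing treatment guards against this. Subjects who have not been told would add a second safeguard.

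Masking looks practicable for randomised subjects. Under Protocol 6.1 and 6.2 both groups receive the same product from the same 367.5 mg vial, and the reconstituted preparations differ in the volume of water added.

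**Working it through.** The main question is one of text, so the check sets the passages side by side.

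**Who is masked in the legible text**

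| Role | Status | Source |
|---|---|---|
| Blinded Evaluator | Masked | Protocol 4.1, 4.4.2 |
| Treating Investigator | Unblinded | Protocol 4.4.2, 4.4.3 |
| Safety assessors | Unblinded | Protocol 4.1, 4.4.2 |
| Sponsor | Unblinded | Protocol 10.9, SAP 2.6 |
| Subjects | Not stated | No legible text |

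The subject row is silence. It is not a statement that subjects are told.

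**Which outcomes depend on the subject, and how they are used**

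| Outcome | Respondent | Shown by group? | Between-group test? |
|---|---|---|---|
| Diary events | Subject | Yes (SAP 2.5, 2.5.4) | No (SAP 2.5: safety is descriptive) |
| Improvement rating | Subject, and separately the Treating Investigator | Yes, with exact 95% intervals per group (SAP 2.4.4) | None planned |
| Folds questionnaire | Probably the subject; the instrument's name is redacted | Yes (SAP 2.4.4) | None planned |
| Satisfaction | Subject | The sentence does not say | None planned |
| Primary endpoint | Blinded Evaluator | Yes (SAP 2.4.3) | None; interval overlap only |

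**Link to the success criteria.** SAP 2.1 lists three. The first (change below zero on both sides of the face in the 8 mL group) and the second (overlap of the two groups' intervals) use the Blinded Evaluator's rating. The third asks for a satisfactory safety profile in the 8 mL group, with no numerical threshold in the legible text. It is the only one that could draw on diary data.

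**Share of the 8 mL group that is not randomised.** Inputs from Protocol 4.1: about 64 randomised 2:1, plus 16 non-randomised on 8 mL.

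- Randomised to 8 mL: 64 × 2/3 = 42.7
- Randomised to 5 mL: 64 × 1/3 = 21.3
- Total on 8 mL: 42.7 + 16 = 58.7

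This agrees with the plan's approximate 60 and 20. The non-randomised share is 16/58.7 = 27.3%, or 16/60 = 26.7% on the plan's rounded figure. About a quarter of the 8 mL group therefore has a dilution fixed by the protocol. SAP 2.2 provides randomised-only sensitivity analyses for the primary endpoint (2.4.3) and the adverse event summary (2.5.2). The legible text of 2.4.4 and 2.5.4 gives none for subject-rated improvement or the diary.

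**The case against.** The strongest reply is that this is a declared design. The title, the synopsis, Protocol 4.1 and SAP 1.1.1 all call the study evaluator-blinded, no text claims that subjects are masked, and nothing is contradicted. That stands: the point is a limit on interpretation with a cheap remedy, not an inconsistency.

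The second reply is redaction. Concealed preparation or plain labelling would naturally sit in the opening of 4.4, in 6.4 or in 6.6, none of which can be read, and part of 4.1 is also blacked out. That stands too, and the point is conditional on it. What remains is that the one legible section on blinding does not mention subjects or refer elsewhere for them.

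The third reply is that little rests on these outcomes, since they are described by group and not tested. This is correct and limits the importance of the point.

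The fourth is that masking would be imperfect. Injected volume may hint at the group, and the Treating Investigator's improvement rating and the safety assessments stay unblinded whatever subjects know. This also stands, and it limits the gain without removing it.

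Two stronger readings are tempting. A reader might infer from the rule against the evaluator discussing treatments with subjects that subjects are told their dilution. The rule only allows for that: it makes equal sense if subjects have merely guessed, or could describe their sessions. A reader might also infer that subjects are face to face with the evaluator at follow-up visits. That is plausible, but the visit descriptions and effectiveness methods are not legible, so it cannot be relied on.

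**Conclusion.** The concern holds in a limited form. On the legible text, assignment is concealed from the Blinded Evaluator only and subjects may know their dilution. Diary events and subject-rated improvement, as shown by group, are open to reporting bias. The folds questionnaire and satisfaction probably are as well, with the reservations that the questionnaire's respondent is not named and the satisfaction sentence does not mention groups.

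The size of any bias cannot be given: the documents contain no figure from which to derive one, and a standard error would describe precision, not bias. A reader might infer that the trial's success is in doubt. The documents do not support that, because the two numerical criteria use the masked evaluator's rating and only the safety-profile criterion is exposed.

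The conclusion assumes that no redacted section already masks subjects. If one does, all that remains is a missing cross-reference in 4.4.2.

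**What to change.** Add to Protocol 4.4.2 that the dilution assigned to randomised subjects is not disclosed to them until their Week 48 assessments are complete. State that vials are reconstituted and syringes prepared out of the subject's sight, and that diaries and other subject papers show no dilution. If a redacted section already provides this, a cross-reference is enough.

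Name the 16 non-randomised 8 mL subjects as the exception, since they cannot be masked. In SAP 2.4.4 and 2.5.4, state that subject-reported results for 8 mL and 5 mL are to be read side by side in randomised subjects.

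The cost is a change of protocol and consent wording and some extra care in handling at each session. There are three downsides: some subjects may guess from the injected volume; subjects already told cannot be masked again; and the Treating Investigator and the safety assessors remain unblinded, so their ratings still need that caveat in the report.
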